4.2. Interim Analysis and Data Monitoring

No interim efficacy analyses are planned.

5. Analysis Populations

The following analysis populations are planned for this study:

- **Safety Population (SAF):** The Safety population will include all subjects who are enrolled and received at least 1 confirmed dose of investigational product (IP). This population will be used for all safety analyses.
- **Intent-To-Treat Population (ITT):** The ITT population will include all randomized subjects. This population will be the primary analysis population for the analysis of efficacy endpoints, along with subject disposition.
- **Modified Intent-To-Treat Population (mITT):** The mITT population includes all randomized subjects with the exception of subjects who missed the Week 8 S-IGA assessment specifically due to novel coronavirus disease-19 (COVID-19) disruptions. This population will be the sensitivity analysis population for the analysis of primary and secondary efficacy endpoints.
- **Scalp Pruritus ITT Population (SPRU4-ITT):** The SPRU4-ITT population is a subset of the ITT population and includes subjects with SI-NRS score ≥ 4 at baseline. This population will be used for the analysis of achievement of a 4-point reduction in SI-NRS score as compared to baseline for this subset of ITT subjects.
- **Scalp Pruritus mITT Population (SPRU4-mITT):** The SPRU4-mITT population is a subset of the mITT population and includes subjects with SI-NRS score ≥ 4 at baseline. This population will be used for the analysis of achievement of a 4-point reduction in SI-NRS score as compared to baseline for this subset of mITT subjects.
- **Pruritus ITT Population (PRU4-ITT):** The PRU4-ITT population is a subset of the ITT population and includes subjects with WI-NRS score ≥ 4 at baseline. This population will be used for the analysis of achievement of a 4-point reduction in WI-NRS score as compared to baseline for this subset of ITT subjects.
- **Pruritus mITT Population (PRU4-mITT):** The PRU4-mITT population is a subset of the mITT population and includes subjects with WI-NRS score ≥ 4 at baseline. This population will be used for the analysis of achievement of a 4-point reduction in WI-NRS score as compared to baseline for this subset of mITT subjects.
- **Pharmacokinetic Population (PK):** The PK population will include all subjects receiving the active drug with sufficient plasma concentrations of roflumilast to define a profile, as determined by the pharmacokineticist. This population will be used for analyses of PK parameters.

6. General Issues for Statistical Analysis

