6.2. Special Handling for COVID-19 Disruptions

In some cases, study visits will have to be delayed/not performed as a result of COVID-19 disruptions (e.g., sites were closed or subjects were under stay-at-home orders). Where possible, study sites may collect post-baseline data from subjects remotely by telephone, traditional mail, and/or email; this will be clearly documented in the source. If possible, sites should adhere to the protocol visit window for remote data collection.

Investigator assessments and subject questionnaires normally completed directly in the electronic patient reported outcomes (ePRO) tablet during on-site visits should be completed on the appropriate paper source documents. The following assessments/questionnaires are approved to be collected via telemedicine/remotely:

- WI-NRS/SI-NRS
- DLQI/CDLQI
- C-SSRS
- PHQ-8/PHQ-A
- Subject Local Tolerability
- PSD

The following assessments cannot be completed via telemedicine/remotely:

- S-IGA/B-IGA
- BSA
- Investigator Local Tolerability
- PASI/mPASI
- PSSI
- Subject Weight

Study visits and procedures must be followed per protocol whenever possible. Any specific changes in study conduct that deviate from the protocol should be communicated to the institutional review board and Sponsor. All protocol deviations which occurred as a result of COVID-19 disruptions (e.g., visits out of window, missed assessments, etc.) will be differentiated from other protocol deviations.

Subjects who were affected by COVID-19 disruptions by either missing their Week 8 visit or being discontinued before having a Week 8 visit due to COVID-19 related disruptions will be excluded from the mITT population, as described in Section 5.

7. Study Subjects and Demographics

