8.2.1. Body Investigator Global Assessment (B-IGA)

The scale, grade, and description for the B-IGA is identical to the S-IGA, as discussed in Section 8.1.

Achievement of a B-IGA score of “clear” or “almost clear” PLUS a 2-grade improvement from baseline at Weeks 2, 4, 8, and 9 will be analyzed similar to the primary efficacy endpoint using CMH test stratified by country, baseline S-IGA category, and baseline B-IGA category, with the exception that missing data will not be replaced (i.e., observed data). Odds ratios and 95% CIs of the odds ratios will be provided. Additionally, the 95% Wilson CIs for proportion of successes in each treatment group will be presented. In addition, the number and percentage of subjects in each category will be summarized by treatment and visit. Only the Week 8 results using the ITT population will be included in the testing strategy.

Analysis of change from baseline in B-IGA scores at Weeks 2, 4, 8, and 9 will be performed using descriptive summaries (mean, median, inter-quartile range) by treatment group and study visit.

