8.2.2. Psoriasis Scalp Severity Index (PSSI)

The PSSI is used to measure the severity of psoriasis, combining the assessment of the severity of scalp lesions and the area of scalp affected into a single score ranging from 0 (no disease) to 72 (maximal disease). The PSSI score will be analyzed as follows:

- Change and percent change from baseline to Weeks 2, 4, 8, and 9 in the PSSI will be analyzed using descriptive summaries and an analysis of covariance (ANCOVA) with terms for country, baseline S-IGA category, and baseline B-IGA category, and baseline PSSI score as a covariate. Statistical comparisons between the treatment groups will be obtained using contrasts. The least-squares (LS) means, standard errors, 95% CIs, and *P* values will be presented.
- Frequencies and percentages of subjects achieving PSSI-50, PSSI-75, PSSI-90, and PSSI-100 will be presented by study week and treatment group. Additionally, these endpoints will be analyzed similar to the primary efficacy endpoint using a CMH test stratified by country, baseline S-IGA category, and baseline B-IGA category, on observed data. Only the PSSI-75 and PSSI-90 at Week 8 using the ITT population will be included in the testing strategy. Odds ratios and 95% CIs of the odds ratios will be provided. Additionally, the 95% Wilson CIs for proportion of successes in each treatment group will be presented.
- Time to achieving PSSI-50, PSSI-75, and PSSI-90 will be summarized using Kaplan-Meier methods and the difference between treatment groups evaluated using the log-rank statistic, and 95% CIs of the median for each treatment group will be presented. In addition, a Cox proportional hazards model that includes the stratification factors will be run and the hazard ratio and associated 95% Wald CIs will be presented. Time to achieving PSSI-50 using the ITT population will also be included in the testing strategy. Time to achieving PSSI-75 or PSSI-90 using the ITT population will not be included in the testing strategy, but will be considered as a supportive analysis.

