9.8. Concomitant Medication

Prior and concomitant medications will be summarized descriptively by treatment, Anatomical Therapeutic Chemical (ATC) Class Level 4, and Preferred Term using counts and percentages.

Prior medications will be presented separately from concomitant medications. Medications that started before the first application of IP will be considered prior medications whether or not they were stopped prior to the first application of study drug. Any medications continuing or starting after the first application of study drug will be considered to be concomitant. If a medication starts before the first application of study drug and continues after the first application of study drug it will be considered both prior and concomitant.

Medications will be coded using World Health Organization (WHO) Drug Global B3, version September 2019.

10. Changes from Planned Analysis

The following analysis populations have been added:

- The mITT population has been added to handle situations where a subject was unable to attend the Week 8 visit or discontinued from the study before the Week 8 visit due to COVID-19 disruptions;
- The SPRU4-ITT and SPRU4-mITT populations have been added to facilitate SI-NRS analysis on the ITT and mITT populations, respectively; and
- The PRU4-ITT and PRU4-mITT populations have been added to facilitate WI-NRS analysis on the ITT and mITT populations, respectively.

These populations are not included in the protocol.

The PP population and associated analyses have been removed at the request of the Sponsor, as they were considered to be uninformative.

Additional exploratory endpoints have been added in the SAP which are not specified in the protocol. They are:

- Change and percent change from baseline in SI-NRS at Weeks 2, 4, and 8
- Change and percent change from baseline in PASI at Weeks 2, 4, 8, and 9
- Change and percent change from baseline in WI-NRS at Weeks 2, 4, and 8

Additionally, odds ratios and 95% CIs of odds ratios for comparisons between treatment groups, and 95% Wilson CIs for proportion of successes in each treatment group for binary outcomes will be provided.

Additional efficacy analyses have been added in the SAP which are not specified in the protocol, as requested by the Sponsor. They are:

- Analysis of S-IGA success based on the following subgroups (both ITT and mITT populations, observed data only):
 - Topical corticosteroids – naïve subjects
 - Topical vitamin D derivatives – naïve subjects

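### For the observed-data Week 8 tests of B-IGA success, PSSI-75, PSSI-90 and nonimputed S-IGA success, mITT as defined in SAP Section 5 contains the same subjects as ITT, so the mITT repeat is not a sensitivity analysis.

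*SAP*

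**What the plan says.** **Population.** SAP Section 5 states: "The mITT population includes all randomized subjects with the exception of subjects who missed the Week 8 S-IGA assessment specifically due to" COVID-19 disruptions. Its role is: "This population will be the sensitivity analysis population for the analysis of primary and secondary efficacy endpoints". SAP 6.2 words the exclusion by visit instead. It removes subjects affected by "either missing their Week 8 visit or being discontinued before having a Week 8 visit due to COVID-19 related disruptions".

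**Assessments.** The Schedule of Events puts S-IGA, B-IGA and PSSI in one row. SAP 6.2 introduces a list with "The following assessments cannot be completed via telemedicine/remotely", and all three are on it.

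**Missing data.**
- SAP 8.2.1 analyzes B-IGA success like the primary endpoint, "with the exception that missing data will not be replaced (i.e., observed data").
- SAP 8.2.2 analyzes the PSSI responder endpoints "using a CMH test stratified by country, baseline S-IGA category, and baseline B-IGA category, on observed data".
- SAP 8.1.1 plans a CMH test of S-IGA success on nonimputed data, leaves all other missing data missing, and repeats its analyses on mITT. SAP 8.2 runs the secondary analyses on both ITT and mITT.
- SAP 6.1.4.1 has a general sentence the other way: in responder analyses other than S-IGA, missing counts as non-response.
- SAP 6.1.5 lets an early-termination or unscheduled value on Days 43-61 stand in for an unavailable Week 8 measurement.

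**Related provisions.** B-IGA success gates all other secondary endpoints (SAP 6.1.3). Protocol 6.3.1 imputes missing S-IGA and B-IGA scores by multiple imputation. The SAP imputes S-IGA only, and Section 10 does not list this as a change. Section 10 does record: "The PP population and associated analyses have been removed at the request of the Sponsor".

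**The concern.** A sensitivity analysis has to be able to give a different answer from the main analysis. An observed-data test at Week 8 already leaves out everyone without a Week 8 value. If mITT removes only people from that group, rerunning the test on mITT cannot change it.

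B-IGA success is the endpoint most exposed, because every later secondary test depends on it. The report would show an ITT result and an mITT result in agreement, and a reader could take the agreement as evidence that missing Week 8 data do not matter. The tipping-point analysis in SAP 6.1.4.2 covers S-IGA only, so under the observed-data rule nothing else in the SAP tests the Week 8 result of these three secondary endpoints against missing data.

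**Working it through.** The plan states no figure for this point, so there is none to reproduce. The check is a set argument, confirmed numerically.

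**Set argument.**
1. Let O be the randomized subjects with a Week 8 value of the endpoint. The observed-data ITT test uses O.
2. Under SAP Section 5, ITT minus mITT contains only subjects without a Week 8 S-IGA. I read a subject with a windowed Day 43-61 S-IGA as having one.
3. S-IGA, B-IGA and PSSI are scheduled together and none can be done remotely. If the Week 8 visit does not take place, all three are missing. I assume that a visit that does take place yields all three.
4. So no subject in ITT minus mITT belongs to O. The mITT test uses O ∩ mITT = O, and the odds ratio, confidence interval and p-value are unchanged. Only the column-header N moves.

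**Numerical confirmation.** One data set of 300 subjects (200:100) was simulated per scenario, with the planning success rates of 32.2% and 9.8% in SAP 3.2. The documents give no missing rate, so COVID-19 missingness of 5-15% per arm and 5% other missingness are assumptions. So are two countries, with 95% of subjects at baseline S-IGA ≥3 and 75% at baseline B-IGA ≥3. The test was the stratified CMH.

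| COVID-19 missing, active/vehicle | Observed data: ITT | Observed data: mITT | Non-response: ITT | Non-response: mITT |
|---|---|---|---|---|
| 5%/5% | OR 6.890, n=268 | identical | OR 6.461 | OR 6.735 |
| 10%/10% | OR 3.093, p=0.0063, n=252 | identical | OR 3.288, p=0.0032 | OR 3.262, p=0.0038 |
| 5%/15% | OR 9.028, n=261 | identical | OR 8.980 | OR 8.445 |
| 15%/5% | OR 5.717, p=0.000027, n=242 | identical | OR 4.440, p=0.00027 | OR 5.148, p=0.00007 |

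The observed-data columns agree in every scenario. The non-response columns do not, so the choice between SAP 6.1.4.1 and SAP 8.2.1/8.2.2 decides whether mITT adds anything.

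**Size of a check that can differ.** With a fraction m missing at random in both arms, counting missing as non-response gives rate × (1 − m):

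| m (assumed) | Active, from 32.2% | Vehicle, from 9.8% | Difference, from 22.4 |
|---|---|---|---|
| 5% | 30.6% (−1.6) | 9.3% (−0.5) | 21.3 |
| 10% | 29.0% (−3.2) | 8.8% (−1.0) | 20.2 |
| 20% | 25.8% (−6.4) | 7.8% (−2.0) | 17.9 |

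The planning rates are IGA rates from the cream trial. They stand in for B-IGA and PSSI rates, which the documents do not give.

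**The case against.** **The SAP may intend non-response.** B-IGA success, PSSI-75 and PSSI-90 are responder analyses, and SAP 6.1.4.1 counts their missing values as non-response. ITT and mITT would then differ. This stands as a real inconsistency. The observed-data reading is the stronger one, because 8.2.1 and 8.2.2 are endpoint-specific and 8.1.1 supports them. But a reader who infers that the two results must agree whatever rule is applied goes further than the documents allow.

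**The two mITT definitions differ.** Protocol 5.5 gives subjects who terminate early the Week 9 procedures, which include S-IGA, B-IGA and PSSI. Under the SAP 6.2 wording, a subject discontinued for COVID-19 with such a value on Days 43-61 could be in the ITT test and out of mITT. This stands. The documents do not say how many such subjects there are, so they cannot be called few.

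**mITT is useful elsewhere.** This also stands. It can change the imputed S-IGA analysis, SI-NRS and PSD (remote collection allowed), and time to PSSI-50 (earlier visits and censoring). Tables 14.2.2.4 and 14.2.3.4 also report Weeks 2 and 4, where subjects excluded from mITT can have values. Dropping those tables is not supported.

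**No decision depends on mITT.** Only ITT enters the testing strategy for these endpoints, so the type I error rate and the primary analysis are unaffected. That limits the severity. It does not turn the repeat into a sensitivity analysis.

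**Equal missingness changes little.** At 10% in both arms the crude odds ratio moves only from about 4.37 to 4.22. That is fair. Such a check need not move the result much, but unlike the mITT repeat it can.

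**Conclusion.** Under the endpoint-specific observed-data rule and the Section 5 definition, the Week 8 mITT repeats of B-IGA success, PSSI-75, PSSI-90 and the nonimputed S-IGA test differ from ITT by exactly zero. They should not be offered as evidence of robustness. The conclusion rests on three conditions: 8.2.1 and 8.2.2 prevail over 6.1.4.1, Section 5 prevails over 6.2, and the three scalp and body assessments are missed together.

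Two further inferences are tempting and are not supported. One is that removing the per-protocol set took away a missing-data check. Protocol 6.1.2 defines that set by compliance and absence of serious deviations, so it was not one. The other is that the protocol already prescribes multiple imputation for PSSI. The synopsis says binary secondary endpoints are analyzed similarly to the primary, but protocol 6.3.1 names only S-IGA and B-IGA as the scores to be imputed.

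The size of any shift under a working check is unknown because no missing rate is stated; the ranges above are illustrations. The change is worth making before unblinding because B-IGA success gates every other secondary endpoint.

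**What to change.** 1. Reconcile SAP 6.1.4.1 with 8.1.1, 8.2.1 and 8.2.2, and state one main missing-data rule for the binary secondary endpoints. Reconcile the mITT definitions in Sections 5 and 6.2, including how a Day 43-61 early-termination or unscheduled value is treated.
2. Keep Tables 14.2.2.4 and 14.2.3.4. Add Week 8 ITT sensitivity analyses of B-IGA success, PSSI-75 and PSSI-90 with missing counted as non-response. If non-response becomes the main rule, make observed data the sensitivity analysis.
3. For B-IGA, add the multiple imputation stated in protocol 6.3.1 by adapting the S-IGA program, or list its omission in Section 10 with a reason. Imputing PSSI is optional. It needs its own model, because the S-IGA program constrains values to integers from 0 to 4 and PSSI runs from 0 to 72.
4. Footnote the Week 8 mITT rows for these tests to say that, under the observed-data rule, they use the same records as ITT.

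The cost is SAP wording and a few added tables. The non-response analysis needs only a recoded input to the existing CMH program; the B-IGA imputation needs modest programming.

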6.1. Statistical Definitions and Algorithms

6.1.1. Baseline

For most efficacy assessments (i.e., S-IGA, B-IGA, PSSI, PASI/mPASI, and % BSA) and all safety assessments except PHQ-8/PHQ-A, the last observation recorded before the first application of study drug will be used as the baseline observation for all calculations of change

from baseline. For other efficacy and safety assessments with a 24-hour or greater recall period (i.e., SI-NRS, WI-NRS, PSD, DLQI/CDLQI, and PHQ-8/PHQ-A), for the previously-named assessments where time is missing (and therefore we are assuming that the assessment was collected before first dose of study drug as per the protocol), or for subject local tolerability (which is expected to be post-dose), the last observation recorded on or before the day of first application of study drug will be used as the baseline observation for all calculations of change from baseline.

For assessments that are collected both before and after application of study drug at the Baseline Day 0 visit, the last observation recorded before the first dose of study will be used as the baseline observation. For assessments collected only after application of study drug, no baseline will be defined (except for subject local tolerability). If the tolerability assessments are not done as per protocol Section 5.1.8, those records will be excluded from the analysis.

6.1.2. Adjustments for Covariates

Subgroup analyses may be generated for the baseline covariates.

[figure not shown]
6.1.3. Multiple Comparisons

To control for multiple comparisons among the secondary endpoints, the following testing plan will be used, as outlined in Figure 1.

Upon demonstration of statistical significance for S-IGA Success at Week 8, the secondary endpoint of B-IGA Success at Week 8 will be tested hierarchically at the 5% significance level.

If the test for B-IGA Success at Week 8 is significant, the α of 0.05 will be split to test 2 families of secondary endpoints. The first family comprise the PSSI-75, which will be tested at the $\alpha = 0.03$ level. If the test of PSSI-75 is statistically significant, then $\alpha = 0.03$ will be used with a Holm testing procedure to test the 4 endpoints of time to success in PSSI-50, change from baseline in Total PSD score at Week 8, change from baseline in Total PSD score at Week 4, and PSSI-90 at Week 8. The remaining $\alpha = 0.02$ will be used to test the second family, comprising the SI-NRS at Week 8, the SI-NRS at Week 4, and the SI-NRS at Week 2. The tests within this second family will be hierarchical, beginning with the endpoint at Week 8, followed by Week 4 and Week 2.

Figure 1: Primary and Secondary Endpoint Testing

Achievement of IGA success is a score of “clear” or “almost clear” plus a 2-grade improvement from baseline.
 SI-WRS Success is a 4-point reduction in SI-NRS among subjects with SI-NRS ≥ 4 at baseline.
 B-IGA = Body-Investigator Global Assessment; EP = endpoint; CFB = change from baseline; PSSI = Psoriasis Scalp Severity Index; S-IGA = Scalp-Investigator Global Assessment; SI-NRS = Scalp Itch - Numeric Rating Scale.

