### 6.3.2 Secondary Endpoints

The Secondary Efficacy Endpoints will include:

[figure not shown]
- B-IGA Success at Week 8, defined as achievement of Body-IGA (B-IGA) score of ‘Clear’ or ‘Almost Clear’ plus a 2-grade improvement from baseline
- PSSI-75 (subjects who achieve a 75% reduction in PSSI from Baseline) at Week 8
- For subjects with Baseline Scalp Itch NRS score  $\geq 4$ , achievement of  $\geq 4$ -point improvement from Baseline in Scalp Itch NRS at Week 8
- For subjects with Baseline Scalp Itch NRS score  $\geq 4$ , achievement of  $\geq 4$ -point improvement from Baseline in Scalp Itch NRS at Week 4
- For subjects with Baseline Scalp Itch NRS score  $\geq 4$ , achievement of  $\geq 4$ -point improvement from Baseline in Scalp Itch NRS at Week 2
- Time to PSSI-50
- Change from Baseline in total PSD score at Week 8
- Change from Baseline in total PSD score at Week 4
- PSSI-90 (subjects who achieve a 90% reduction in PSSI from Baseline) at Week 8

To control for multiple comparisons among the secondary endpoints, the following testing plan will be used:

Upon demonstration of statistical significance for S-IGA Success at Week 8, the secondary endpoint of B-IGA Success at Week 8 will be tested hierarchically at the 5% significance level.

If the test for B-IGA Success at Week 8 is significant, the  $\alpha$  of 0.05 will be split to test 2 families of secondary endpoints. The first family will be comprised of the PSSI-75, which will be tested at the  $\alpha = 0.03$  level. If the test of PSSI-75 is statistically significant, then  $\alpha = 0.03$  will be used with a Holm testing procedure to test the 4 endpoints of time to success in PSSI-50, CFB in Total PSD score at Week 8, CFB in Total PSD score at Week 4, and PSSI-90 at Week 8. The remaining  $\alpha = 0.02$  will be used to test the second family, comprised of the Scalp WI-NRS at Week 8, the Scalp WI-NRS at Week 4, and the Scalp WI-NRS at Week 2. The tests within this second family will be hierarchical, beginning with the endpoint at Week 8, followed by Week 4 and Week 2. .

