4.1. Introduction

Data processing, tabulation of descriptive statistics, calculation of inferential statistics, and graphical representations, will be performed primarily using SAS (release 9.4 or higher). If the use of other software is warranted for analyses conducted by Premier Research, the final statistical methodology report will detail what software was used for what purposes.

Continuous (quantitative) variable summaries will include the number of subjects (n) with nonmissing values, mean, standard deviation (SD), median, minimum, and maximum.

Categorical (qualitative) variable summaries will include the frequency and percentage of subjects who are in the particular category or each possible value. In general, the denominator for the percentage calculation will be based upon the total number of subjects in the study population for the treatment group, unless otherwise specified.

Unless otherwise indicated, all statistical tests will be conducted at the familywise $\alpha=0.05$ significance level using 2-tailed tests, and *P* values will be reported. Corresponding 95% confidence intervals (CIs) will be presented for statistical tests. Details for splitting the familywise α to control for multiple comparisons will be discussed in Section 6.1.3.

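### The written plan fixes the two secondary families at 0.03 and 0.02 with no rule for passing alpha on; confirm against Figure 1 and, if absent, add one

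*SAP*

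**What the plan says.** SAP 4.1 sets a "familywise $\alpha=0.05$ significance level using 2-tailed tests". Under SAP 6.1.3, a significant S-IGA result opens B-IGA success, which "will be tested hierarchically at the 5% significance level". If that is also significant, the 0.05 "will be split to test 2 families of secondary endpoints":

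- **Family 1.** PSSI-75 comes first, "which will be tested at the $\alpha = 0.03$ level". If it is significant, the same 0.03 "will be used with a Holm testing procedure to test the 4 endpoints of time to success in PSSI-50", the other three being the two PSD changes (Weeks 8 and 4) and PSSI-90.
- **Family 2.** The remaining 0.02 "will be used to test the second family, comprising the SI-NRS at Week 8", then Week 4 and Week 2, in that fixed order.

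Protocol 6.3.2 gives the same levels. There the 0.02 "will be used to test the second family, comprised of the Scalp WI-NRS at Week 8" and the two later itch tests; the label differs, but I read it as the Scalp Itch NRS responder endpoint in the protocol's own list. The protocol synopsis repeats the scheme.

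None of the three texts says what becomes of the 0.03 or the 0.02 after its family is completely rejected. Each document also has a testing figure (SAP Figure 1, Protocol Figure 3). Only captions and footnotes are available here, and the footnotes define endpoints and abbreviations only.

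**The concern.** On the written rules, SI-NRS can never be tested above 0.02 and PSSI-75 can never be tested above 0.03, however strong the other family is. Suppose all five family 1 tests succeed and SI-NRS Week 8 gives p = 0.03. Week 8 fails and Weeks 4 and 2 are not tested, although the 0.03 that family 1 no longer needs lies unused. A rule with the same order and starting split that hands on a fully rejected family's alpha would have allowed that rejection within the same 0.05. What is at stake is power for secondary claims. SAP 3.2 asserts sufficient power for most secondary endpoints but gives no figure.

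**Working it through.** **1. The plan's own figure.** 0.03 + 0.02 = 0.05. With independent families the error is 1 − 0.97 × 0.98 = 0.0494. The split controls familywise error as intended.

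**2. Does passing keep the 0.05?** The rule examined: a family rejected in full at its starting level hands its whole alpha to the other, which is then tested at 0.05.
- *Both families contain a true null.* Neither can be fully rejected without a false rejection, so no alpha moves before the first error. That error occurs at 0.03 or 0.02, giving at most 0.03 + 0.02 = 0.05.
- *Only one family contains a true null.* That family is tested at 0.05 at most, and its internal procedure (PSSI-75 then Holm, or the fixed sequence) controls error at that level.

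Simulation of the eight tests after the B-IGA gate (400,000 runs, zero correlation) agrees. The standard error near 0.05 is √(0.05 × 0.95 / 400,000) = 0.0003.

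| True nulls | Without passing | With passing |
|---|---|---|
| All eight | 0.0496 | 0.0496 |
| Family 2 only | 0.0195 | 0.0493 |
| Family 1 only | 0.0300 | 0.0498 |

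No simulated trial lost a rejection. None can, because each family is tested at its starting level or higher.

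**3. Upper limit of the gain.** This is single-test power at the starting level against 0.05:

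power = Φ{[|p₁ − p₀| − z(1−α/2)·SE₀] / SE₁}, with SE₀ from the pooled rate and SE₁ from the separate rates.

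For an assumed subset of 140 vs 70 and rates of 50% vs 30%:
- Pooled rate = (70 + 21)/210 = 0.4333; SE₀ = 0.0725; SE₁ = 0.0692.
- α = 0.02: (0.2 − 2.326 × 0.0725)/0.0692 = 0.45, so power is 67.4%.
- α = 0.05: (0.2 − 1.960 × 0.0725)/0.0692 = 0.84, so power is 79.8%.

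| Test and assumption | Starting level | At 0.05 |
|---|---|---|
| SI-NRS Week 8, 140 vs 70, 50% vs 30% | 67.4% | 79.8% |
| SI-NRS Week 8, 160 vs 80, 40% vs 25% | 48.8% | 63.9% |
| SI-NRS Week 8, 120 vs 60, 50% vs 30% | 59.4% | 73.3% |
| PSSI-75, 200 vs 100, 40% vs 25% | 66.2% | 73.9% |

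The differences run from about 8 to 15 points. At the only rates the documents give (32.2% vs 9.8%, 200 vs 100, SAP 3.2), power at 0.02, 0.03 and 0.05 is 98.9%, 99.3% and 99.7%, so there the limit is under 1 point.

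**4. Gain actually realised.** Alpha moves only after the other family is fully rejected. Simulated results, with the marginal power of each test at 0.05 assumed and correlation from 0 to 0.7:

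| Assumed power of each test | SI-NRS Week 8 | PSSI-75 |
|---|---|---|
| All 80% | 68% to 70–71% | 74% to 75–76% |
| All 90% | 82% to 84–86% | 86% to 87–88% |
| Family 1 99%, family 2 80% | 68% to 79–80% | little change |
| Family 1 80%, family 2 99% | little change | 74% to 79–80% |

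In the step 3 scenarios, let the four Holm endpoints have the same power as PSSI-75 and the later itch tests the same as Week 8. SI-NRS Week 8 then gains 1.3 to 1.6 points (140 vs 70), 1.6 to 3.7 (160 vs 80) and 1.5 to 2.2 (120 vs 60); PSSI-75 gains 0.6 to 2.3. The gains are small because all five family 1 tests succeed in only about 12% to 39% of trials.

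**The case against.** The strongest reply is that nothing is wrong. A fixed split is simple and valid, protocol and SAP agree on it, and the primary and B-IGA tests are untouched. Not passing alpha also has an effect of its own: when one family is truly effective, the actual error in the other stays at 0.02 or 0.03 instead of rising towards 0.05. All of this stands. It makes the point an efficiency improvement, not the correction of an error. The extra conservatism goes beyond the familywise 0.05 that the SAP sets itself.

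A second reply is that the rule may already exist. SAP 6.1.3 presents the plan as outlined in Figure 1, and arrows between the families are what such a drawing could carry. This also stands. A reader might infer that alpha is never passed on, but the documents available support only that the text states no such rule. If the figure does show passing, the text should say so, because it names fixed levels.

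A third reply concerns size. A reader might take the step from 67% to 80% as the expected gain. It is not; it is a ceiling, approached only when the other family is near certain to succeed.

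**Conclusion.** The point holds as a low-cost improvement, subject to a check of Figure 1. The written split is valid but can leave alpha unused, and two-way passing keeps familywise error at or below 0.05 without losing any rejection. The gain is about 1 to 4 points when the families have similar power and about 6 to 11 points when one is near certain to succeed. The single-test differences of 8 to 15 points are upper limits in the scenarios shown.

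These sizes rest on assumed effects, subset sizes and correlations, because the documents give no secondary effect sizes and do not state how many subjects will have a baseline SI-NRS of at least 4.

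A reader might also infer that the itch endpoints are the weakest-powered claims, since they have the smaller share and a subset of subjects. The documents do not rank the endpoints. The Holm step starts at 0.03/4 = 0.0075, stricter than 0.02, and PSSI-90 is a harder response than PSSI-75.

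**What to change.** Check SAP Figure 1 and Protocol Figure 3 for passing between the families. If it is there, state the rule in SAP 6.1.3. If it is not, add before unblinding, leaving the order and starting split unchanged:

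> If PSSI-75 and all four Holm endpoints are rejected, 0.03 passes to the SI-NRS sequence, which is then tested at 0.05. If all three SI-NRS endpoints are rejected, 0.02 passes to the PSSI-75/Holm family, which is then tested at 0.05.

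Make Figure 1 match, and list the rule in SAP section 10 as a change from the protocol, since Protocol 6.3.2 and the synopsis carry the fixed split. The cost is a few sentences and no new data. Added after unblinding, the rule would be post hoc.
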